12.5.7 ADDITIONAL EXPLORATORY ANALYSES

The use of dry eye lubricants will be summarized by Treatment group at one month.

12.6 SAFETY ENDPOINTS AND ANALYSIS

12.6.1 DESCRIPTIVE ANALYSES

All adverse events, measures of pain and discomfort, changes in IOP, and changes in BCVA (EDTRS) will be tabulated by visit and treatment group.

12.6.2 PRIMARY SAFETY ENDPOINT

The primary safety endpoint is the incidence of ocular adverse events.

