1 PROTOCOL SYNOPSIS

Protocol Title	Randomized, Controlled Trial to Evaluate the Safety and Effectiveness of the TearCare® System in the Treatment of the Signs and Symptoms of Dry Eye Disease
Protocol ID Number	06196
Study Device	TearCare® System
Control Group	LipiFlow® Thermal Pulsation System
Primary Objective	To demonstrate the safety and effectiveness of a single TearCare® treatment compared to a single LipiFlow treatment to treat the signs and symptoms of dry eye disease in adult patients.
Study Design	Prospective, randomized, single-masked, multi-center non-inferiority, post-market study.
Primary Effectiveness Endpoints	Mean Change from baseline to 1 month in: 
○ Tear Break-Up Time (TBUT)○ Total Meibomian Gland Secretion Score
Secondary Effectiveness Endpoints	Mean Change from baseline to 1 month in: 
○ Ocular Surface Disease Index (OSDI) score○ Corneal staining scores○ Conjunctival staining scores○ Symptom Assessment in Dry Eye (SANDE) scores○ Eye Dryness Score○ Number of Meibomian Glands Yielding any liquid○ Number of Meibomian Glands Yielding clear liquid
Primary Safety Endpoint	
○ Device-related adverse events
Secondary Safety Endpoints	
○ Discomfort/pain during treatment○ Change in best corrected visual acuity (ETDRS)○ Change in intraocular pressure (IOP)

Inclusion Criteria	
1. At least 22 years of age2. Reports dry eye symptoms within the past 3 months3. Reports having to use artificial tears or lubricants regularly over the past month to relieve dry eye symptoms.4. OSDI Score of 23-795. TBUT of ≤ 7 seconds in both eyes6. Meibomian gland obstruction in both eyes based on a total Meibomian Gland Secretion Score ≤ 12 in each eye.7. At least 15 glands in each lower eyelid should be expressible, with a sterile cotton swab, at the slit lamp.8. Best corrected visual acuity of 20/100 or better in both eyes.9. Willing and able to comply with the study procedures and follow-up10. Willing and able to provide informed consent11. English-speaking
---------------------------	---

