6.2 SAFETY ENDPOINTS

- **Primary Safety Endpoint**
 - Device-related adverse events (all adverse events will be recorded)
- **Secondary Safety Endpoints**
 - Discomfort/pain during treatment
 - Change in best corrected visual acuity (ETDRS)
 - Change in intraocular pressure (IOP)

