7.1 STUDY DEVICE AND CONTROL ARM

In this study, treatment with the TearCare System (study device) will be compared with treatment with the LipiFlow System (control arm).

TearCare treatment includes an in-office 15 minute bilateral treatment session with the TearCare System immediately followed by manual expression of the meibomian glands using the Clearance Assistant device. Subjects randomized to TearCare will receive one in-office TearCare treatment on study Day 0.

The LipiFlow System is indicated for use as follows:

The LipiFlow System is intended for the application of localized heat and pressure therapy in adult patients with chronic cystic conditions of the eyelids, including Meibomian Gland Dysfunction (MGD), also known as Evaporative Dry Eye or Lipid Deficiency Dry Eye.

Subjects randomized to LipiFlow will receive the LipiFlow procedure bilaterally conducted per the device instructions for use. The LipiFlow procedure will be performed in-office on study Day 0.

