10 ADVERSE EVENTS (AES)

Adverse Events are defined below. Adverse events that occur in the eye during the trial, whether they are considered to be device related or not, must be documented in the subject’s records. Non-ocular adverse events do not need to be recorded as adverse events unless they meet the definition of serious adverse event or are believed to be related to the study device or a study procedure. Date of the event, its severity, treatment (if any) and the assessed relationship of the event to the study device will be recorded on the Adverse Event Form. Conditions which exist at the time the subject is

enrolled do not need to be recorded as adverse events unless they increase in severity during the study.

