22.3.3 SAFETY

For a safety sample of size 238 TearCare eyes (from Cohort 1 and Cohort 2) (since the expected AE rates are quite low there is unlikely to be any meaningful correlation between eyes), if the true incidence rate of ocular adverse events is 2.0% or less then the upper 95% one-sided confidence limit for the AE rate will be less than 6% with probability approximately 0.95. In other words, the power to reject a null of 6% if the true rate is 2.0% is 95%.

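### The primary safety endpoint is device-related adverse events in the synopsis and Section 6.2 but ocular adverse events in Section 12.6.2 and SAP 22.2.2, and neither set contains the other

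*Combined protocol and SAP*

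**What the plan says.** **Definition A, device-related.** The synopsis lists the primary safety endpoint as "Device-related adverse events". Section 6.2 repeats this and adds in parentheses that all adverse events are recorded. That addition concerns data collection; it does not widen the endpoint.

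**Definition B, ocular.** Section 12.6.2 states: "The primary safety endpoint is the incidence of ocular adverse events". SAP Section 22.2.2 repeats the sentence. Neither place adds a relatedness condition.

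**Analysis.** Sections 12.6.3 and 22.2.3 both compute the incidence of ocular events as a proportion of subjects. Section 12.6.3 also adds an event rate that 22.2.3 omits. Both call for a summary by treatment group; neither sets a hypothesis or success threshold.

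**Sizing.** SAP Section 22.3.3 states its precision for 238 TearCare eyes, "if the true incidence rate of ocular adverse events is 2.0% or less", with a 6% bound on the upper one-sided 95% limit.

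**Collection.** Under Section 10, ocular events, "whether they are considered to be device related or not, must be documented in the subject’s records". Non-ocular events need not be recorded "unless they meet the definition of serious adverse event or are believed to be related to the study device or a study procedure". In addition, "the assessed relationship of the event to the study device will be recorded on the Adverse Event Form". Section 7.1 applies the term study device to TearCare and calls LipiFlow the control arm.

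**The concern.** A primary endpoint should have one definition. Here two are in force, and they differ in substance. Safety is named in the study objective, and the data are meant to support a changed indication, so a reader of the report will look for one primary safety incidence. As written, the report could present either rate as primary and cite the protocol for it.

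There are two further loose ends. The device-related version has no clear meaning in the control arm, because relatedness is recorded against the study device and only TearCare carries that name. The precision statement is written for eyes, while the endpoint is counted in subjects.

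**Working it through.** **1. Which events count under each definition (from Section 10)**

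| Event | A: device-related | B: ocular | Recorded? |
|---|---|---|---|
| Ocular, device-related | yes | yes | yes |
| Ocular, not device-related | no | yes | yes |
| Non-ocular, device-related | yes | no | yes |
| Non-ocular, unrelated to device or procedure, not serious | no | no | not required |

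Rows two and three show that the sets overlap and that neither contains the other.

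**2. Reproducing the plan's own figure (SAP 22.3.3)**

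Inputs: n = 238 eyes, true rate 2.0%, bound 6%, one-sided 95% limit.

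The exact (Clopper-Pearson) upper limit is below 6% when P(X ≤ x | n, 0.06) < 0.05.
- x = 8: P(X ≤ 8 | 238, 0.06) = 0.049, upper limit 5.98%. Passes.
- x = 9: P(X ≤ 9 | 238, 0.06) = 0.090, upper limit 6.51%. Fails.
- Power = P(X ≤ 8 | 238, 0.02) = **94.8%**.

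The stated 95% is reproduced. It is conditional on a rate of 2.0%. With the same n and rule, other assumed rates give:

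| Assumed true rate per eye | 1% | 2% | 3% | 4% | 5% |
|---|---|---|---|---|---|
| Probability that the upper limit is below 6% | 99.9% | 94.8% | 71.2% | 38.6% | 15.5% |

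The documents assume a rate for ocular events only. They give none for device-related events, so nothing in them shows where definition A would fall in this table.

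**3. The same statement on the endpoint's own unit**

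The 238 eyes are 119 TearCare subjects × 2, and Section 12.7 gives about 119 in that group. The endpoint counts subjects with any event.
- x = 2: P(X ≤ 2 | 119, 0.06) = 0.024, upper limit 5.20%. Passes.
- x = 3: P(X ≤ 3 | 119, 0.06) = 0.069, upper limit 6.39%. Fails.
- Power = P(X ≤ 2 | 119, 0.02) = 0.0903 + 0.2194 + 0.2642 = **57.4%**.

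This reads both 2% and 6% as per-subject rates. If they are per-eye rates and the eyes are independent, as 22.3.3 in effect assumes, the per-subject equivalents are 1 − 0.98² = 3.96% and 1 − 0.94² = 11.64%. Then x ≤ 7 passes, and the power is P(X ≤ 7 | 119, 0.0396) = 89.9%, but for a bound near 12% of subjects. If the true rate is 3.96% and the bound stays at 6% of subjects, it is P(X ≤ 2 | 119, 0.0396) = 14.6%.

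**4. Illustration of the definitional difference (counts assumed)**

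The SAP's ADD2 95% interval is p = (x + 2)/(n + 4), p ± 1.96·√(p(1 − p)/(n + 4)), with n = 119.
- x = 2: p = 4/123 = 3.25%, interval 0.1% to 6.4%.
- x = 6: p = 8/123 = 6.50%, interval 2.1% to 10.9%.

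If 2 subjects had a device-related event and 6 had any ocular event, the reported upper limit would be 6.4% or 10.9% depending on the section followed. The counts are not in the documents, and the gap follows entirely from choosing them.

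**The case against.** The strongest reply is that an analyst working from Section 12 and the SAP meets only one definition. Every analysis and sizing section uses ocular events, and no analysis is written for device-related events. Safety is descriptive, all adverse events are tabulated by group under 12.6.1 and 12.6.3, and relatedness is recorded, so a selective headline would be visible. All of this stands, and it limits the consequence. It does not remove the conflict: the synopsis and Section 6.2 state the endpoint without qualification, and nothing ranks one definition above the other.

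Three stronger readings are tempting, and the documents do not support them.
- *Device-related attribution is made by staff who know the arm.* Section 9.8 lists AE assessment among the tasks of the Masked Assessor, who may not randomise or treat. Section 10.3 has the investigator record the relationship. Who attributes is therefore unclear; unmasked attribution is possible but not established.
- *The trial's conclusion depends on the choice.* SAP 22.1.1 defines success as non-inferiority on both tear break-up time and gland score. Safety is not part of that rule.
- *The 22.3.3 calculation is valid only for ocular events.* It is a binomial statement that holds for any per-eye event at or below 2.0%. It is labelled ocular, and the documents do not show that device-related events would exceed that rate.

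**Conclusion.** The contradiction is real and sits in a primary endpoint. It changes which incidence is reported as the primary safety result. It does not change the study success decision, and ocular events are collected under either reading. Its numerical effect on the reported rate cannot be derived from the documents; the 6.4% versus 10.9% contrast is an illustration on assumed counts.

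One figure can be stated. The 95% in 22.3.3 is correct for 238 eyes but does not carry over to a per-subject endpoint. With 119 TearCare subjects, a 2% per-subject rate and a 6% per-subject bound, it is about 57%. That figure assumes all 119 subjects contribute and that 2% and 6% are meant per subject; the alternative readings above range from about 15% to about 90%. The point should be corrected before analysis.

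**What to change.** Before analysis, use one definition throughout.

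1. Amend the synopsis and Section 6.2 to the proportion of subjects with at least one ocular adverse event, and state the same in 12.6.2 and 22.2.2. The ocular version is the natural choice because 12.6.3, 22.2.3 and 22.3.3 are already written for it, though the documents do not compel it. The subject proportion is the measure that 12.6.3 and 22.2.3 share; the event rate in 12.6.3 can stay as supportive.
2. Add device-related adverse events, ocular or not, as a pre-specified secondary safety endpoint in the synopsis, 6.2, 12.6.4 and 22.2.4. State that relatedness in the control arm means relatedness to LipiFlow, and state who makes the attribution.
3. Restate 22.3.3 per subject, saying whether 2% and 6% are per-subject rates. If they are, the exact figure is about 57% for 119 subjects.

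Cost: wording edits in several sections and a less favourable stated precision for safety. The primary endpoint needs no new data. For the secondary endpoint, confirm that the relatedness entry on the adverse event form has been completed against LipiFlow in that arm.

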12.6.3 PRIMARY SAFETY ANALYSIS

All adverse events will be reported by treatment group and AE category. Any serious adverse events will be completely described in the study report. The primary safety endpoint will be summarized for each treatment group.

We will compute the incidence of ocular events in two ways: first as a simple proportion, counting the number of subjects with any event (that is, counting the first event per person in either eye), then as an incidence rate, counting all events including repeated events per subject.

12.6.4 SECONDARY SAFETY ENDPOINTS

The secondary safety endpoints include:

- Discomfort/pain during treatment
- Change in best corrected visual acuity (ETDRS)
- Change in intraocular pressure (IOP)

These endpoints will be summarized by treatment group and visit.

12.7 SAMPLE SIZE CALCULATION

Up to 100 Cohort 1 subjects and 138 Cohort 2 subjects, approximately 119 in the TearCare group and 119 in the LipiFlow group, will be enrolled and randomized in the study. Sample size was calculated to provide more than 90% power to meet both the TBUT and MEIB effectiveness endpoints in Cohort 2 and sufficient precision around the

adverse event estimates. The sample size also takes into account an estimated 10% dropout rate. Details of the sample size calculation can be found in Appendix B.

12.8 DEVIATION FROM THE STATISTICAL PLAN

Any deviations from the statistical plan will be noted in the final report.

13 MONITORING PROCEDURES

Sight Sciences or contract research organization (CRO) personnel will monitor the study in a manner consistent with FDA regulations, good clinical practices and the clinical research standards adopted by Sight Sciences. Study monitoring will involve the following elements:

- Site Qualification: Sight Sciences or CRO personnel will meet with investigators and clinical study staff prior to the initiation of the study in order to review the adequacy of the subject population, facilities, and equipment with respect to the needs of the study, and to familiarize the investigator with the study protocol.
- Site Initiation: Sight Sciences or CRO personnel will meet with the investigator(s) and clinical study staff when the site is ready to begin enrolling subjects in order to train them in how to properly select subjects, perform the study procedure, and record study data. This visit will include, but not be limited to a review of the following:
 - Detailed review of the protocol
 - Informed consent procedures
 - Randomization procedures
 - Instruction in how to use the TearCare System
 - Instruction in how to perform study procedures
 - Guidance in how to administer questionnaires to subjects
 - Procedures for maintaining masking of study personnel
 - Records and reports
- Interim Monitoring: Sight Sciences or CRO personnel will visit the clinical site routinely during the study to review charts and to perform source document verification, to ensure proper adherence to the study protocol, and to review regulatory documents. Interim monitoring visits and telephone consultation will occur as necessary during the course of the study to ensure the proper progress and documentation of the study findings.
- Study Closure: At the conclusion of the trial there will be a study closure visit during which several actions, including but not limited to the following, will be performed:

- A final inspection of the study binder
- Accountability and return of all devices and study materials to the sponsor
- Discussion of record retention requirements with the investigator
- Close-out notification to the IRB

14 DATA AND QUALITY MANAGEMENT

14.1 DATABASE MANAGEMENT

The study database will be designed using an electric data capture (EDC) system that is compliant with 21 CFR Part 11 and relevant guidance documents. The EDC will be developed and maintained by an independent, qualified data management firm.

The database will incorporate time-stamped audit trails, protection of human subjects, restricted access, and data security at the component level. Each database module, including each individual eCRF, will be validated by conducting a series of standard tests that demonstrate usability and correctness of the database system. The database will be maintained on an ongoing basis and will be routinely backed up.

14.2 SUBJECT IDENTIFICATION

The subjects will be identified by a five digit subject number composed of a one-digit study identification number, a two digit center identification number followed by a two digit sequential subject number. The subject identification will be assigned when informed consent is obtained. In this way, information contained in the study records will be kept as confidential as possible.

14.3 SUBJECT ACCOUNTABILITY

All subjects randomized and treated in this clinical investigation shall be monitored for the duration of the investigation. The clinical investigation shall be considered completed when all subjects that have been enrolled in the investigation have reached the final reporting period, excluding subjects who were withdrawn.

14.4 CONFIDENTIALITY

All medical records associated with the clinical investigation will be made available for review by Sight Sciences personnel, its contract research organization (CRO) and governmental/regulatory agencies involved. The results of the study may be published in the future for scientific and marketing purposes, but the identity (name) of each

subject will not be revealed. All records will be stored in a secure area at the investigator's facility, the CRO, the data management firm and at Sight Sciences, Inc.

14.5 SOURCE DATA AND CASE REPORT FORMS

Source data will be entered into a validated electronic system at each site by trained personnel in accordance with 21 CFR Part 11 requirements. Electronic entries will be 100% verified against corresponding source data at the sites and queried/corrected if needed to the extent possible. Medical site records serve as source data. In addition, data that are collected exclusively for the purpose of this study and not normally recorded in the subjects' medical records can be collected directly on the study worksheets provided by the sponsor and these study worksheets will serve as the source data.

Source data and study worksheets are to be maintained at the site in the subject records or in the medical records. All entries must be made in black or blue ink and changes must be made by strike-through only with date and initials or signature. All source documents must be completed and signed by the authorized study personnel (e.g., study coordinator). No "white-out" is to be used on the source documents.

14.6 RETENTION PERIOD

Clinical sites are to retain any and all clinical trial material (documentation, photographs, etc.) for a period of two years from the date the marketing application is approved or two years after the investigation has been discontinued, or as directed by their institutional document retention requirements, whichever is the longest. After that time, the items must be returned to Sight Sciences for archiving. Unused medical devices are to be returned to the sponsor at the conclusion of the enrollment period.

15 PROTOCOL MODIFICATIONS AND DEVIATIONS

Protocol modifications may occur during the study. Each will be approved by the sponsor before implementation. Each will undergo Institutional Review Board (IRB) review and approval, as necessary.

Any deviations from this protocol intended to protect the life or physical well-being of a subject in an emergency are to be reported to Sight Sciences, Inc. as well as the IRB as soon as possible, and no later than 5 working days after the emergency occurred.

All protocol deviations will be documented using the Protocol Deviation form.

16 DEVICE FAILURES AND MALFUNCTIONS

All device failures or malfunctions should be recorded on the Device Deficiency Form and reported to Sight Sciences Customer Service [REDACTED]).

If the TearCare or LipiFlow procedure cannot be completed due to a product failure or malfunction, the procedure may be rescheduled for a different day. Every effort should be made to reschedule the procedure within the next 7 calendar days of the Baseline visit.

17 ETHICAL CONSIDERATIONS

17.1 DECLARATION OF HELSINKI

This study shall be conducted in accordance with the Declaration of Helsinki (Appendix D).

17.2 INSTITUTIONAL REVIEW BOARDS (IRB)

The study shall not begin at a site until approval has been obtained from the reviewing IRB. It is the Investigators' responsibility to obtain and maintain written approval of the study protocol and Informed Consent documents from the appropriate IRB. It is also the Investigators' responsibility to notify that body about any amendments to these documents and to follow the IRBs rules regarding the reporting of Adverse Events and Protocol Deviations related to the device and/or this study. Copies of all written approvals (identifying the study, the submitted and approved documents and the date reviewed) and the approved versions of the documents must be provided to Sight Sciences or its CRO.

The Investigators must file all correspondence with the IRB and forward copies of such correspondence to Sight Sciences.

17.3 INFORMED CONSENT FORM (ICF)

An Informed Consent template that covers all protocol procedures and follows GCP Guidelines will be prepared by Sight Sciences and made available to each Investigator. The Investigator may adapt these templates to the requirements of the local IRB and of the institution where the study is conducted, but any revisions made to the ICF must be submitted to the sponsor for review prior to submission to the IRB. A copy of each IRB-approved ICF version is to be made available to Sight Sciences and its CRO. The approved, IRB-stamped ICF is to be kept in its full length in the study Regulatory Binder.

Original, signed ICFs are to be maintained in the subject's study records and must be made available for monitoring review.

17.4 PUBLIC LISTING OF STUDY

The study will be listed on the NIH website www.clinicaltrials.gov.

18 STUDY ADMINISTRATION

18.1 DEVICE ACCOUNTABILITY

With each shipment of study devices, Sight Sciences will include a Packing List that will give the amount shipped and the lot numbers. This packing list must be reconciled by the investigational site with the contents of the shipment and then recorded on the Device Accountability Logs (these logs are contained within the regulatory binder at the site). All study products at the site must be stored in a secured/locked area. When study devices are used, returned or disposed of, their disposition (including the disposition and date of disposition) must be recorded on the Device Accountability log.

Device reconciliation activities will also be conducted periodically in conjunction with site monitoring visits. The investigator must maintain accurate records of the receipt and disposition of all devices shipped by Sight Sciences.

